Nicotine replacement therapy. Participants in both arms will receive a free supply of nicotine patches (Habitrol Patches, Novartis, Denmark) via post office mail at two separate occasions: first 4-week supplies of 21mg and then 2-week supplies of each 14mg and 7mg together. Those who smoke between 5-9 cigarettes will receive 14mg for 6 weeks and then 7mg for 2 weeks. Those who report difficulty using patches due to skin reactions and who earn a high score (≥ 7) on the Fagerstrom Test for Nicotine Dependence^{38,39} will receive nicotine gums (2 or 4mg, Habitrol Gums, Novartis, Denmark). Adherence to nicotine patches and gums will be monitored asking number of patches and gums that they have used for the past 7 days. Prior to receiving nicotine patches and gums, participants will be instructed as to correct usage and possible side effects of the products, and which side effects that they should report immediately. Nicotine replacement products will be used in the study in accordance with their FDA approved labeling.

Video Watching. Participants in both arm will be randomly assigned to either the SNC or attention-control interventions and accordingly receive the videos of either quitting smoking or being diagnosed with HIV infection, respectively. Participants in the control arm will also receive the SNC videos of quitting smoking right after the last data collection that is 3-month follow-up post-quit.

Saliva Cotinine Test. Participant who report abstinence at 3-month follow-up will receive two NicAlert™ test kits in 2-3 days via express mail. They will conduct the test at home and hence, there is no transportation of samples. Research staff will inform that participants should not open sealed test strips before the test. She/he will also inform them that they should not eat or drink for at least 30 minutes before the test. The staff person will assist them in testing by providing following step-by-step instructions.

1. Take out collection tube and funnel from the white vinyl bag.
2. Put the funnel in a collection tube.
3. Spit into the collection tube through the funnel until the tube is half full.
4. Discard the funnel and close the tube with a cap until you hear click.
5. Tear off the sealed white wrap and take out the test strip inside
6. Put the strip on the flat surface.
7. Squeeze the collection tube while holding it upside down

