Specific Aim 2: Determine the feasibility and acceptability of an SNC intervention for smoking cessation for WLHIV by assessing 1) the rate of **recruitment and retention** for feasibility and 2) the degree of **transport and identification** for acceptability in the narrative enhancement. We will identify and describe the time to recruitment and any barriers. We will also describe reasons for study refusal and compare refusal rates by age ranges and number of cigarettes smoked per day, using χ^2 and t-tests. We will compare attrition rates at each follow-up by intervention condition and abstinence status, using Mann-Whitney tests. Subjects will complete an Exit Survey, rating their overall satisfaction with the intervention that they have. They will also rate their experience with the SNC videos, using a 7-point Likert-type scale.⁴⁵ In addition, the Measure of Narrative Engagement will be used as a quantitative indicator of 1) narrative understanding, 2) attentional focus, 3) narrative presence, and 4) emotional engagement.¹⁹

Specific Aim 3: Establish an effect size of HIV-tailored smoking cessation and SNC interventions in comparison with the HIV-tailored smoking cessation intervention only for WLHIV by comparing 30-day abstinence rates at 6-month follow-up. We will evaluate the balance of baseline demographics and smoking behavior between the two arms, using t-tests or Mann-Whitney tests for continuous variables and χ^2 tests for categorical variables. We will examine differences in continuous or 7-day point-prevalence abstinence rates between the two arms, using the χ^2 tests. Individuals who are not available at follow-up assessments or yield a cotinine test result higher than the cutoff level of 0 (cotinine level 0-30mg/ml) will be all treated as smoking. We will calculate an effect size by comparing 30-day abstinence rates at 6-month follow-up point between the two arms. We will also explore longitudinal logistic regression models under the framework of generalized linear mixed models to examine the relationships between abstinence status and intervention conditions over time.

PROTECTION OF HUMAN SUBJECTS

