Protection against Risks: To prevent or minimize nicotine withdrawal symptoms, we will provide via secured post office mails nicotine patches to all subjects and gums to those who earn a high score (≥ 7) on the Fagerström Test for Nicotine Dependence.³⁸ [name] and students who are trained will counsel subjects, focusing on coping strategies that have been found effective in dealing with the withdrawal symptoms. For example, students will educate smokers a variety of behavioral strategies to manage the symptoms such as 4Ds (Distract, Drink water, Deep breathe, and Discuss). Students will educate them about how and where to apply a nicotine patch, what to do if the patch comes off, how to handle common issues such as taking a shower, and how to dispose of a used patch. Students will also explain that they should chew nicotine gum slowly, until they feel a tingling sensation or a 'peppery' taste (usually after about 10 chews). Then rest it for one minute under their tongue, or between their cheek and teeth. This allows the nicotine to pass through the lining of their mouth. They should continue this 'chew - rest' sequence for 30 minutes, then throw away the gum. They should avoid eating and drinking 15 minutes before, and during, use of the gum (except for water). Acidic foods or drinks, such as orange juice, coffee, beer and soft drink, interfere with the amount of nicotine passing through the lining of their mouth from the gum.

During sessions, counselors will educate side effects of nicotine patches/gums and their proper managements. They will provide an emergency contact number ([name] cell phone) to all subjects and instruct them to call the number if they experience any serious side effects of the medication such as nausea and vomiting. Counselors will monitor every subject weekly for the first four weeks of the medication and monthly thereafter during the remaining 4-weeks of the medication and at 1- and 3-month follow-ups. Nicotine intake during pregnancy is associated with an increased risk for spontaneous abortion, increased prenatal mortality, and with low infant birth weights. The safety of nicotine in nursing infants has not been clearly established. Thus, we will **exclude** pregnant women, nursing mothers, and women who are not using an acceptable form of birth control from the study.

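### The cotinine rule makes no provision for nicotine-product use at the 3-month test, so some women abstinent from cigarettes could be counted as smokers

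*Protocol*

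**What the plan says.** Protocol, Data Analysis, Specific Aim 3, and the same section of the SAP give an identical outcome rule. Women who cannot be reached at follow-up, or who "yield a cotinine test result higher than the cutoff level of 0 (cotinine level 0-30mg/ml) will be all treated as smoking". Neither document adds an exception or a sensitivity analysis for nicotine-product use.

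The protocol's Nicotine replacement therapy paragraph gives patches to both arms. The standard supply is "first 4-week supplies of 21mg and then 2-week supplies of each 14mg and 7mg together". For lighter smokers it is: "Those who smoke between 5-9 cigarettes will receive 14mg for 6 weeks and then 7mg for 2 weeks". Some women also "will receive nicotine gums (2 or 4mg, Habitrol Gums, Novartis, Denmark"); no quantity, duration or end is given for gum. The same paragraph monitors adherence by the "number of patches and gums that they have used for the past 7 days". That item does not appear in Table 1 and plays no part in the outcome rule.

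The cotinine test is scheduled once, at 3 months post-quit, and only for women who report abstinence.

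**The concern.** Cotinine shows exposure to nicotine, not to cigarettes. In a trial that supplies nicotine, a rule scoring every reading above level 0 as smoking can overturn a true report of abstinence when the woman is still using a trial product. The test is given only to self-reported abstainers, so each product-driven positive moves one woman from success to failure.

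At stake is the 3-month abstinence comparison in a pilot of 25 per arm, where one to three women are visible in the result. If product use is not recorded at the test, these positives cannot later be told apart from relapse.

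**Working it through.** **Inputs.** Abstinence rates of 45.5% vs 20%, two-sided 5%, 80% power, 52 per arm required and 25 per arm planned (Protocol, Power and Sample Size); patch durations (Nicotine replacement therapy); test at 3 months post-quit (Saliva Cotinine Test and Table 1). The share g of true abstainers who read above level 0 because of nicotine products is not in the documents. It is an assumption, varied from 0 to 0.30.

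**1. The plan's own figure.** Pooled two-proportion formula, no continuity correction:

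n = [1.960 × √(2 × 0.3275 × 0.6725) + 0.842 × √(0.455 × 0.545 + 0.20 × 0.80)]² / 0.255² ≈ 51.97, so 52 per arm. The stated figure reproduces and is not in dispute.

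**2. Timeline.** Standard patches: 4 + 2 + 2 = 8 weeks. Lighter smokers: 6 + 2 = 8 weeks. Three months is about 13 weeks. If patches start on the quit day (assumption), the gap to the test is 13 − 8 = 5 weeks, so on-schedule patch use should not cause positives. Supply can reach the test in a woman who starts about 5 weeks late. It can also do so if she starts on time but, at one patch per day of use (assumption), wears patches on fewer than 8/13, or about 62%, of days.

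**3. Gum.** Two passages bear on its length and two on who receives it.
- Length: the supply text gives product and strength only. Under Protection against Risks, in a paragraph that opens with both products, "Counselors will monitor every subject weekly for the first four weeks of the medication and monthly thereafter during the remaining 4-weeks of the medication". That implies 4 + 4 = 8 weeks of medication, but the sentence concerns monitoring, does not name gum and sets no limit on supply.
- Recipients: under Nicotine replacement therapy they are "Those who report difficulty using patches due to skin reactions and who earn a high score" (7 or more) on the Fagerström test, which requires both conditions. Under Protection against Risks the plan is "nicotine patches to all subjects and gums to those who earn a high score", which requires the score alone. The two passages conflict and must be reconciled; the size of the gum group depends on the answer.

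**4. Illustrative size, equal g in both arms.** Observed rate = true rate × (1 − g). Women moved per arm = 25 × true rate × g.

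| g | SNC arm | Control | Difference (points) | Risk ratio | Women moved, SNC / control |
|---|---|---|---|---|---|
| 0 | 45.5% | 20.0% | 25.5 | 2.275 | 0 / 0 |
| 0.10 | 41.0% | 18.0% | 23.0 | 2.275 | 1.1 / 0.5 |
| 0.20 | 36.4% | 16.0% | 20.4 | 2.275 | 2.3 / 1.0 |
| 0.30 | 31.9% | 14.0% | 17.9 | 2.275 | 3.4 / 1.5 |

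The factor (1 − g) cancels in the risk ratio; the difference shrinks.

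**5. Unequal g.** With g = 0.20 in the SNC arm only, the difference is 0.455 × 0.80 − 0.20 = 16.4 points. With g = 0.20 in control only, it is 0.455 − 0.20 × 0.80 = 29.5 points. The bias can go either way.

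**6. Reach of the rule.** Specific Aim 3 takes its effect size from 30-day abstinence at 6 months. Table 1 ends at 3 months and schedules cotinine only there. How the rule enters the 6-month comparison is therefore undefined.

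**The case against.** The strongest case against is that the exposed group may be close to empty. The monitoring sentence can be read as an 8-week course for both products, and the protocol ties product use to approved labeling. On the narrower gum criterion few women would receive gum, and active skin disease is already an exclusion. Counselors are to monitor every woman at the 1- and 3-month follow-ups, so the product question may in effect be planned for the right visit. A strict biochemical rule is also a deliberate safeguard, and classifying positives by self-report weakens it.

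Much of this stands. It limits the size of the problem, and it is a reason to keep the strict rule as the main analysis. It does not remove the gap: whatever course was intended, the rule does not say how to handle a woman who is using a product when tested.

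A reader might infer more than the text supports:
- **That gum continues indefinitely, so abstinent women would be misclassified.** The 8-week reading is available, and the documents do not show how often gum use gives a reading above level 0. The supportable word is could.
- **That the bias runs against the SNC arm.** Both arms receive the same counseling and products, and the documents give no reason to expect different use by arm.
- **That the next trial must be larger by a calculable amount.** The share affected has no source. The 20% comes from an ongoing study whose classification rule is not stated, so reducing it again may count the same loss twice. The effect size is also to come from a 6-month assessment to which this rule has no defined application.

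**Conclusion.** The point holds as a minor, inexpensive improvement. The rule as written makes no provision for nicotine-product use at the test, in a trial that supplies nicotine to both arms. Women who used products late, intermittently or beyond the intended course could be scored as smoking while abstinent from cigarettes.

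The size is unknown and may be small. The 0–30% range is purely an assumption and treats the planning rates as true rates; within it the 3-month difference would lie between 25.5 and 17.9 points if use is equal by arm. The 5-week gap rests on starting treatment on the quit day. No direction of bias and no effect on a later trial's sample size should be claimed. Confidence that the effect is material is low.

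**What to change.** - State that the existing past-7-day patch and gum question is asked at the 3-month cotinine test, and add it to Table 1.
- Keep the stated cotinine rule as the main analysis.
- Pre-specify one sensitivity analysis that classifies self-reported abstainers with current nicotine-product use by their self-report, and report their number by arm.
- Reconcile the two passages on who receives gum, and state the intended gum quantity and duration, so that expected exposure at the test can be judged.

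The cost is one existing question placed at a scheduled contact and one extra line of analysis, with no new staff or procedure. The downside is that a few women are classified without biochemical support in the sensitivity analysis, which should be read as a check on the main result and not as a replacement for it.

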- Phase 1. Development of Narrative Video:** We will first develop narrative videos in collaboration with community organizations of WLHIV in Boston. The video will be filmed in person at the University of Massachusetts Boston.
- Phase 2. A Randomized Controlled Trial (RCT) of a Story Telling Narrative Communication Intervention:** We will conduct a two-arm RCT assigning participants at a ratio of 1:1 to either one of the two arms (**Experimental:** HIV-tailored plus SNC interventions vs. **Control:** HIV-tailored plus attention-control interventions). Both arms will have eight weekly sessions of a 30-minute HIV-tailored cessation intervention (cognitive behavioral therapy plus nicotine patches). The experimental arm will receive three 5-minute SNC videos (testimonial stories about successful quitting), each per month between the first and third month of quitting, whereas the control arm receive three 5-minute attention control videos (women talking about being diagnosed with HIV) at the same monthly interval. However, participants in the control arm will also receive the SNC videos talking about successful stories of smoking cessation right after the last follow-up assessment (3-month follow-up post-quit). The overall flow of the study is illustrated in Figure 1. All research-related procedures will be conducted remotely.

Figure 1. The overall design of the study

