2. Phase 2. An RCT of a Storytelling Narrative Communication Intervention: Counseling contents will be primarily drawn from a cognitive behavioral therapy foundation, which is guided by Bandura's Social Cognitive Theory.^{33,34} Within the theory, self-efficacy, that is, the conviction that one can successfully execute a behavior required to produce the outcome is viewed as the most influential determinant of the behavior and its appraisals are based on the following four: performance accomplishment, vicarious experience, verbal persuasion, and physiological state. Participants will have eight weekly counseling sessions and the duration of the sessions is approximately 200-240 minutes over 8 weeks. They will be counseled to enact small changes that are accomplishable, which will be the source of performance accomplishment. Both HIV-tailored and SNC interventions will augment self-efficacy via vicarious experience and verbal persuasion. The NRT will further increase self-efficacy by targeting physiological state. To prevent attrition, we will execute several strategies, including tracking subjects at least every month and providing incentives for follow-up tests. Counselors will proactively call participants prior to each therapy session and confirm the appointment a few hours before the session. A research assistant (RA) will conduct all follow-up assessments via telephone calls and video call for saliva cotinine tests. Regardless of smoking status, participants will receive a Visa gift card worth \$25 at each follow-up assessment (post-quit 1, 2, and 3 months). Any participants who report abstinence at post-quit 3 months will be asked to do the salivary cotinine test via a video call on a smartphone and receive another Visa gift card worth \$25 upon completion of the test. Those who complete all three follow-up assessments will receive one time bonus of a gift card worth \$100.

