Individual counseling before the quit day. The main focus of the first session will be assessing each participant's readiness for smoking cessation and accordingly setting the target quit day. The day will be usually set between the third and fifth sessions. Pre-quit sessions will be focused on preparing participants for the quit day, which includes counseling to delay smoking the first cigarette at least 30 minutes after awakening and expanding smoking free areas inside the house until complete smoking ban is established at least a week before the target quit day. As a form of knowledge development, the effects of smoking on people with HIV will also be highlighted during the first session. The second session will be geared toward explaining neurobiological changes associated with nicotine addiction and immediate health benefits of quitting. The session (usually the third or fourth one) right before the quit day will be focused on explaining the underlying treatment mechanism of transdermal nicotine patches and gums. During the session, correct usage of nicotine patches and gums, their possible side effects, and how to manage the side effects will be educated. Skills training for situational smoking temptations will be provided with role plays so that participants can learn coping strategies that are known to be effective for avoiding lapses and relapses.

Individual counseling after the quit day. Post-quit sessions will vary by individual needs depending on abstinence status and the severity of nicotine withdrawal symptoms. Thus, the number of cigarettes smoked for the past 7 days will be assessed at each post-quit session using the 7-day Timeline Follow-back Scale.³⁵ Minnesota Nicotine Withdrawal Scale will be assessed prior to counseling at each session and participants will be counseled accordingly depending on severity of nicotine withdrawal symptoms.³⁶ Participants will be counseled to utilize the 4D (Deep breathing, Drink Water, Distract, and Delay) behavioral strategies when they experience nicotine withdrawal symptoms.³⁷

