8. Have at least eight full drops of saliva drip from the tube onto the white padded area of the test strip (right below the three green arrows).

A research staff member will closely monitor the whole process via the video call. She/he will be blind to treatment condition. The person can read the result of the test when the blue line on top of the strip disappears, which usually takes 20-30 minutes. She/he will ask participants to take a photo of the strip right after the video call and send it to her/him. Then, the person will share the photo with other research staff to validate one's reading of the result.

Study Measures and Assessment Procedures: Baseline and three follow-up assessments will be conducted by telephone survey. All measures (see Table 1 below) have been tested and validated for use with WLHIV. Those who report abstinence will receive NicAlert® test kits at 3-month follow-up by a post office mail right before the follow-up assessments. As described above, participants will be guided step-by-step to perform the test while the whole process being closely monitored by research staff via a video call.

Table 1 Assessment schedule of study measures

Variables	Measure	Base	1M*	2 Ms*	3 Ms*
Demographics	Demographic Datasheet	✓			
History of HIV Infection	Year of the diagnosis, CD4 cell count, and viral load	✓			
HIV-medication Adherence	CASE Medication Adherence Scale ⁴⁰	✓			
History of Smoking and Quitting	Smoking and Quitting Datasheet	✓			
Stigma and Secrecy	HIV-related Stigma Scale ⁴¹	✓			
Alcohol Use	Alcohol Use Disorders Identification Test (AUDIT) ³²	✓			
Depression	Patient Health Questionnaire-9 ⁴²	✓			✓
Anxiety	Generalized Anxiety Scale-7 ⁴³	✓			✓
Nicotine Dependence	Fagerström Test for Nicotine Dependence ^{37,38}	✓	✓	✓	✓
Self-Efficacy	Self-Efficacy Scale ⁴⁴	✓	✓	✓	✓
Nicotine Withdrawal	Minnesota Tobacco Withdrawal Scale ³⁶		✓	✓	✓
Narrative Engagement	The Measure of Narrative Engagement ¹⁹			✓	✓
Program Evaluation	The Client Satisfaction Questionnaire ⁴⁵		✓	✓	✓
Abstinence or Cigarette Consumption	7-day Timeline Follow-back Smoking Behavior ³⁵		✓	✓	✓
	Saliva Cotinine Test (NicAlert®)				✓
Treatment Fidelity	Intervention Fidelity and Competence Scale ([name], unpublished work)		✓	✓	✓

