Power and Sample Size: This study aims to establish a preliminary effect size. In the currently ongoing study, abstinence rate for the video arm was 75.5% at post-quit 1 month but dropped to 20.0% at post-quit 3 months. For a two-sided test at a 5% significance level, 52 participants are required per arm to have 80% of power for abstinence rates 45.5% vs. 20%.⁴⁶ As a pilot study, we will recruit 50 subjects (25 per arm).

Data Analysis: Data analysis will be done in collaboration with the **U54 Research Design and Analysis Core**. Prior to data entry, data will be reviewed and double-checked for completeness and coding errors first by a research assistant and then by a data manager. An intention-to-treat analysis strategy will be used for cessation outcomes with missing values.

Specific Aim 1: Identify storytelling narrative communication (SNC) intervention components that are rated high in transport and identification* for use as an enhancement to an HIV-tailored smoking cessation intervention (*Narrative Understanding, Attentional Focus, Narrative Presence, and Emotional Engagement). Through two local networks of Black WLHIV in which [name] is a key collaborator, we will identify volunteers who have quit smoking and film them while they tell their story of quitting. We will ask them structured questions based on Bandura's Self-Efficacy Model to elicit the story components. When the film is edited effectively for clarity of content and length, it will be tested for acceptability using a mix-methods approach. Using focus groups the film will be shown and participants will be asked what they liked the most and the least about the film. These data will be analyzed for saturation through thematic analyses.

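### The Aim 3 effect size is defined as 30-day abstinence at 6 months, but follow-up ends 3 months after quitting and the follow-up smoking measure looks back 7 days, so it cannot be computed as written

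*Protocol*

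**What the plan says.** Specific Aim 3 is the same in the Data Analysis section of the protocol and in the SAP. Each names the 6-month, 30-day endpoint twice, first when stating the aim and again when describing the calculation: "We will calculate an effect size by comparing 30-day abstinence rates at 6-month follow-up point between the two arms". The same paragraph separately plans chi-square comparisons of continuous abstinence or 7-day point prevalence, without a time point, and exploratory longitudinal mixed models.

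The operational sections of the protocol describe something else:

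- **Study Measures and Assessment Procedures:** "Baseline and three follow-up assessments will be conducted by telephone survey". The Table 1 columns are baseline and months 1, 2 and 3.
- **Video Watching:** controls are sent the storytelling (SNC) videos "right after the last data collection that is 3-month follow-up post-quit". Research Design, Phase 2 says the same.
- **Study Procedures, Phase 2:** incentives for follow-up are tied to months 1, 2 and 3 after quitting.
- **Table 1, abstinence row:** "7-day Timeline Follow-back Smoking Behavior" at months 1, 2 and 3, and saliva cotinine at month 3. Nothing else is listed.
- **Power and Sample Size:** the control-arm planning rate is the one that "dropped to 20.0% at post-quit 3 months" in the ongoing study.

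**The concern.** The endpoint fails on time point and on look-back window, and each failure is enough on its own. Changing 6 months to 3 would still leave a 30-day window with no instrument. Adding a 30-day question would still leave no 6-month contact at which to ask it.

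Study Aims lists an effect size for subsequent grant applications as the third purpose of the study, and this is the only effect size the plan defines. Someone would have to settle the window and the time point later, possibly with the results in view, which a prespecified plan is meant to prevent. The Project Description also argues that the intervention should sustain abstinence for 6 months or longer. A reader therefore cannot tell whether the endpoint or the schedule is the mistake. Nor does the plan say that the pilot leaves that hypothesis untested.

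**Working it through.** **1. The plan's own figure.** Power and Sample Size gives 52 per arm for 45.5% vs 20%, two-sided 5%, 80% power. With pooled variance and no continuity correction, mean rate 0.3275 and difference 0.255:

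n = [1.960·√(2·0.3275·0.6725) + 0.842·√(0.455·0.545 + 0.20·0.80)]² / 0.255² = 51.97, rounded up to 52.

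This reproduces exactly, so the sample-size arithmetic is not in question. The 20% is a rate at 3 months after quitting, not at 6.

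**2. Time point.** Could 6 months be counted from the start of counseling? The protocol says of the quit day: "The day will be usually set between the third and fifth sessions". Sessions are weekly.

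- Quit day: 2 to 4 weeks after session 1.
- Last assessment: 2 + 13 = 15 to 4 + 13 = 17 weeks after session 1.
- Shortfall against 26 weeks: 26 − 17 = 9 to 26 − 15 = 11 weeks.

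Neither origin gives a 6-month observation.

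**3. Look-back window.** At month 3 the timeline covers 7/30 = 23% of the named window. Post-quit counseling sessions also ask about the past 7 days, so consecutive weekly answers might be joined. Session 8 is 7 weeks after session 1, while the month-3 assessment is at weeks 15 to 17, a gap of 8 to 10 weeks. The 30 days before month 3 begin about 4.3 weeks before that assessment, so all of them fall after the last session. Joining sessions could approximate a 30-day figure near month 1 for women who quit early (sessions 4 to 8 after a session-3 quit cover 5 × 7 = 35 days), but not at month 3 or later. The plan gives cotinine no role in establishing 30 days of abstinence.

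**4. The missing-data rule applied literally.** Aim 3 counts anyone unavailable at follow-up as smoking. At 6 months nobody is assessed, so the result would be 0/25 vs 0/25: a difference of zero and an undefined odds ratio.

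**5. What the available replacement would give.** This takes 7-day abstinence at month 3, 25 per arm and the plan's rates. Because the plan does not state the abstinence window behind its 20%, using it for 7-day abstinence is an assumption.

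- Difference = 0.455 − 0.20 = 25.5 points.
- SE = √(0.455·0.545/25 + 0.20·0.80/25) = 0.1277.
- Wald 95% CI = 0.255 ± 1.96·0.1277 = 0.5 to 50.5 points.
- Newcombe 95% CI (from Wilson limits) = −0.5 to 47.3 points.
- Odds ratio = (0.455/0.545)/(0.20/0.80) = 3.34.
- Cohen's h = 2·arcsin√0.455 − 2·arcsin√0.20 = 0.55.

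**The case against.** The strongest reply is that this looks like wording left over from a longer design. A usable endpoint is already present: Aim 3 plans a 7-day comparison, month-3 cotinine is scheduled, and the planning rate is a month-3 rate. On that view little is lost, and saying the analyst must invent a replacement goes too far.

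Part of this stands. The plan does contain a collectable endpoint. What it does not do is name that endpoint as the effect size or attach a time point to it. It offers it as an either/or with continuous abstinence, which monthly 7-day recalls cannot establish. Where the wording came from does not matter to a reader who finds the 6-month phrase four times alongside a rationale built on 6-month abstinence.

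A second reply is that the interval, odds ratio and h in the working describe a small sample, not the harm done by the mismatch. That is right, and they are given only to show what the replacement would deliver. They are also sensitive to rounding, since 45.5% of 25 is 11.375 women. With 11/25 vs 5/25 the Wald interval is −1.0 to 49.0 points, and with 12/25 vs 5/25 the Newcombe interval is 1.8 to 49.6. Whether an interval crosses zero should not be read as a finding.

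Figure 1 and the note to the Table 1 asterisks are not visible in the text reviewed. Neither is likely to change the conclusion, because the prose twice calls the 3-month assessment the last.

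**Conclusion.** The concern holds and must be fixed. The Aim 3 effect size, as defined in both documents, has no data at its time point for any of the 50 planned participants, and no scheduled item covers its window (7 of 30 days at month 3). This is an error in the plan as written, not a missing detail, and the SAP repeats it instead of resolving it.

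The conclusion rests on the stated schedule and on the usual timing of the quit day. It does not depend on the assumed abstinence rates. The count of 50 follows Subjects and Power and Sample Size; the Project Description says 60, which makes no difference here. Aims 1 and 2, the 7-day comparisons at months 1 to 3 and the mixed models stand.

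**What to change.** In Aim 3 of both documents, rewrite both sentences so that the effect size is the between-arm difference in 7-day point-prevalence abstinence 3 months after quitting, verified by the scheduled saliva cotinine test, reported with a 95% confidence interval. Recast the second sentence in full, because substituting the phrase alone leaves it ungrammatical. Add one sentence saying that this pilot does not test abstinence at 6 months or later.

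If a 30-day window is preferred, keep it at month 3 and add a 30-day recall item to the month-3 interview and to Table 1.

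If the sponsor keeps 6 months, the assessment schedule, the cotinine schedule and the release of the storytelling videos to controls right after month 3 must all be reconciled with it. With that release unchanged, a 6-month comparison would be of immediate versus delayed storytelling videos.

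Two neighboring points can be settled in the same edit: whether continuous abstinence stays in the chi-square comparison, and how a woman who reports abstinence but does not complete the cotinine test is classified.

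**Cost.** The 7-day version needs wording only, with no added contacts, items or participants. The 30-day version needs one added interview item. The downside is an endpoint at a shorter term than the plan names and, with 7 days, a shorter abstinence window.
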